University of Kansas Medical Center
RESEARCH PROTOCOL INVOLVING HUMAN SUBJECTS
TEMPLATE WITH GUIDANCE

Version date: April 25, 2019

Principal Investigator: [name], MS

Study Title: An open label trial of cryoneurolysis for improvements in pain, activities of daily living and quality of life in patients with ankle osteoarthritis.

I. Purpose, Background and Rationale

A. Aim and Hypotheses

This will be an open-label trial to describe the effects of cryoneurolysis with iovera on symptom relief in patients with painful Kellgren-Lawrence (KL) grade 2–4 ankle osteoarthritis (OA). The Foot and Ankle Outcome Score (FAOS) subscales will be used to assess outcomes at 6, 12 and 24 weeks after treatment.

The aim of this study is to assess clinically significant long-term symptomatic relief with cryoneurolysis in people with unilateral ankle osteoarthritis (OA).

Depending on the location of pain, we will treat either 1) the Superficial Fibular Nerve (SFN), Sural Nerve (SN) and Saphenous Nerve or 2) the deep fibular nerve with cryoneurolysis using the iovera device. The primary study endpoint, clinically significant improvement in pain 12 weeks after each treatment, will be assessed using the FAOS-Pain subscale.

The secondary outcomes will be improvement in quality of life (FAOS-QoL), activities of daily living (FAOS-ADL) and Numerical Rating Scale (NRS) for pain.

The tertiary outcome will be improvement in physical performance measures (40m fast-paced walking test, Standing Balance Test).

We hypothesize that people with painful ankle OA will experience significant improvement in pain, activities of daily living, quality of life and physical performance for at least 12 weeks following treatment. Based on research done using iovera in patients with knee osteoarthritis, we anticipate that it will have a greater magnitude and duration of analgesic effect along with significantly fewer adverse events compared with the rates reported for standard of care therapy (i.e. corticosteroid injection).^{1,2}

Specific Aim 1: To determine the extent of pain relief after cryoneurolysis of nerves innervating the ankle joint in patients with ankle osteoarthritis.

Primary Hypothesis 1: Cryoneurolysis of nerves innervating the ankle joint in patients with ankle OA results in reduction in ankle pain (FAOS-Pain) detectable at the following post-treatment time points:

- a) 6 weeks
- b) 12 weeks (primary outcome)
- c) 24 weeks

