Post-treatment, the axon regenerates until it re-innervates to the sensory receptor for predictable restoration of nerve function. The effect on the nerve is temporary. The duration of the pain relief depends on the individual and the location of the nerve being treated. In general, nerves regenerate at a rate of approximately 1.0-1.5mm per day.⁶ Therefore, we hypothesize a duration of relief of ankle pain of approximately 90 days.

Preliminary Data: A recent randomized, double-blind, sham-controlled, multicenter trial (17 sites) with a 6-month follow-up was conducted in 180 patients with mild-to-moderate knee OA. This study demonstrated that a single treatment of the infrapatellar branches of the saphenous nerve with iovera[°] resulted in a reduction in the pain and symptoms for at least 90 days.¹ Compared to the sham group, patients who received iovera[°] treatment had a statistically significant greater change from baseline in the WOMAC pain subscale score at Day 30 (p=0.0004), Day 60 (p=0.0176), and Day 90 (p=0.0061) post-treatment. Patients deemed WOMAC pain responders at Day 120 continued to experience a statistically significant treatment effect at Day 150. Most expected side effects were mild in severity and resolved within 30 days. The incidence of device- or procedure-related adverse events were similar in the two treatment groups with no occurrence of serious or unanticipated adverse device effects (ADE).

This clinical trial will be the first to systematically evaluate the symptomatic and functional benefits of cryoneurolysis for patients suffering from painful ankle OA. Patients are more likely to seek medical care when they are experiencing symptoms, have reduced activity and/or functional limitation. Therefore, finding that an affordable, safe treatment could alleviate symptoms and improve activities of daily living while avoiding the side effects of pharmacological and surgical therapies, holds promise to improve quality of life and reduce health care expenditures.

iovera[°] Device and Treatment Procedure

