The cryoneurolysis mechanism of action is well-understood and established in prior studies.⁵ Results of a recent study demonstrate that cryoneurolysis can alleviate the pain and symptoms of knee OA for up to 90 days¹. Pharmacologic and surgical options for ankle OA are limited. Using cryoneurolysis in patients with ankle OA could potentially provide immediate symptomatic relief with a greater duration of analgesia and a lower rate of side effects. These potential benefits could reduce the need for both clinic and injection visits when compared to other available treatment modalities, thereby reducing patient and provider burden and health care expenditures.

II. Research Plan and Design

A. Study Objectives: The goal of this study is to evaluate the efficacy of cryoneurolysis for improving ankle symptoms and function. Specifically, this study will measure changes in pain, activities of daily living, quality of life and physical performance at 6, 12 and 24 weeks after each superficial and deep treatment.

B. Study Type and Design:

This is a single-site, open-label study of participants with painful ankle OA assigned to undergo cryoneurolysis of either the Superficial Fibular Nerve (SFN), Sural Nerve (SN) and Saphenous Nerve, or the Deep Fibular Nerve (DFN) using ultrasound-guided cryoneurolysis. Subjects will initially undergo diagnostic nerve blocks using 1% lidocaine with epinephrine for either the superficial nerves or the DFN to confirm analgesia prior to the cryoneurolysis procedure.

We will evaluate responder status with NRS at clinic visits 6 weeks, 12 weeks and 24 weeks following treatment as well as NRS via web-form or phone calls (per subject preference) at 3, 9 and 18 weeks. "Non-responders" being defined as anyone reporting less than 20% pain relief with respect to their baseline NRS scores. For subjects who become non-responders, we will treat the other nerve group with iovera at their next clinic visit (e.g. if a subject becomes a non-responder 9 weeks after superficial nerves are treated, then at 12 week follow-up, the participant will be offered treatment of the deep fibular nerve).

Figure 2 depicts the flow of how participants will be treated and potentially offered an alternative treatment if their initial treatment fails to provide durable benefit.

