All participants will be assigned to undergo cryoneurolysis using iovera. FAOS (Pain, ADL, QoL), NRS for pain and physical performance test (40 m fast paced walking test, standing balance test) data will be collected at baseline, 6 weeks, 12 weeks and 24 weeks. A 24-week follow-up duration was selected to detect meaningful differences from standard of care and long-term effects, while minimizing the variability that may occur further out from baseline. Differences between each of the three follow-up time points for each of the interventions (superficial and deep) and baseline will be assessed using one-sample t-tests or repeated measures analyses, as appropriate. This will control for study-wide alpha level to account for multiple comparisons as well as 6-week and 24-week analyses. A soft-lock of the database will occur after the 6- and 12-week time-points.

- B. Outcome:** We expect statistically significant and clinically meaningful improvement in pain, activities of daily living, quality of life and physical performance with iovera[®] in people with ankle OA at 12 weeks post-treatment.
- C. Study results to participants:** The study will be registered on www.clinicaltrials.gov and results posted upon completion of the study.
- D. Publication Plan:** Results will be submitted for presentation at an appropriate conference and for publication in an appropriate journal for the topic of study.

VI. Bibliography / References / Literature Cited

5. Trescot AM. Cryoanalgesia in interventional pain management. *Pain Physician* 2003;6:345-60.

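### Read plainly, each nerve-group estimate mixes first courses with second courses given only after non-response, and the second course has no defined baseline

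*Combined protocol and SAP*

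**What the plan says.** The outcome is defined per treatment in several places.

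- Objectives (II.A): "this study will measure changes in pain, activities of daily living, quality of life and physical performance at 6, 12 and 24 weeks after each" of the two nerve-group treatments.
- Primary endpoint (I.A): "clinically significant improvement in pain 12 weeks after each treatment, will be assessed using the FAOS-Pain subscale". Section II.E words the same endpoint simply as 12 weeks post-treatment.
- Hypothesis 3a is stated for each cryoneurolysis treatment.
- Analysis (V.A): the tests concern "Differences between each of the three follow-up time points for each of the interventions (superficial and deep) and baseline".

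The first nerve group follows the site of pain: "Depending on the location of pain, we will treat either 1) the Superficial Fibular Nerve (SFN), Sural Nerve (SN) and Saphenous Nerve or" (with the deep fibular nerve as the alternative, I.A). The second course is conditional (II.B): "For subjects who become non-responders, we will treat the other nerve group with iovera at their next clinic visit". A non-responder is anyone with "less than 20% pain relief with respect to their baseline NRS scores".

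The second schedule table in II.E gives treatment 2 its own 3- to 24-week follow-up. FAOS, NRS and performance tests are listed on the treatment day and again at weeks 6, 12 and 24.

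No readable section separates first from second courses in the analysis, or says whether second-course change is taken from the original baseline or from the value at treatment 2.

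**The concern.** An estimate for the deep nerve, built as V.A is worded, would draw on two kinds of course. Some patients had the deep nerve treated first because their pain pointed there. Others had the superficial nerves treated first, had too little relief, and then had the deep nerve added. The superficial estimate has the same structure in reverse. The second kind of course differs in who receives it (non-responders only), in why that nerve group is used (it was not the initial choice by location), and in what it follows (an earlier treatment). Some patients would also contribute to both estimates.

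The pooled figure would then be neither the effect of treating a nerve group first nor the effect of adding it after failure. Week-12 FAOS-Pain is affected, because I.A attaches it to each treatment. With no control group, nothing else in the design can separate the two.

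**Working it through.** **The plan's own figures.** The plan states neither a re-treatment rate nor a superficial/deep split, so there is no figure to reproduce on this point. The sample size in II.C counts participants, not courses: 32/(1 − 0.20) = 40.

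**Share of second courses.** Let S and D be the numbers treated first on the superficial and deep nerves, and r the proportion re-treated. All three are assumptions, with S + D = 40.

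- Deep: r·S/(D + r·S)
- Superficial: r·D/(S + r·D)

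| S/D | r | Deep | Superficial |
|---|---|---|---|
| 20/20 | 0.25 | 5/25 = 20% | 5/25 = 20% |
| 20/20 | 0.50 | 10/30 = 33% | 10/30 = 33% |
| 30/10 | 0.25 | 7.5/17.5 = 43% | 2.5/32.5 = 8% |
| 30/10 | 0.50 | 15/25 = 60% | 5/35 = 14% |

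**Direction of the bias.** A simulation on assumed inputs (NRS mean 6.5, SD 2, entry at 5 or more; first-course relief mean 2, SD 2; same mean effect for the second nerve group) gave 36% to 39% non-responders at a single check. Two effects then oppose each other:

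- If treatment 2 did nothing, non-responders would still appear to improve by 0.18 to 0.78 NRS points (reliability 0.9 to 0.5) when the score that triggers re-treatment is also the new baseline.
- If response is correlated across courses, the true second-course effect in non-responders falls from 2.0 to 1.1–1.2 points (correlation 0.5) or 0.55–0.76 points (correlation 0.8).

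The net bias cannot be signed. These figures are for NRS, not FAOS-Pain, and only illustrate the mechanism.

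**Overlap with the first treatment.** Section I.B states: "Therefore, we hypothesize a duration of relief of ankle pain of approximately 90 days". Days are counted from the first treatment.

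| Re-treated at | Days left to 90 | Second-course week 6 | Second-course week 12 |
|---|---|---|---|
| Week 6 (day 42) | 90 − 42 = 48 | 42 + 42 = 84 | 42 + 84 = 126 |
| Week 12 (day 84) | 90 − 84 = 6 | 84 + 42 = 126 | 84 + 84 = 168 |

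Only one second-course clinic visit falls inside 90 days: week 6 after a week-6 re-treatment. The week-3 NRS call in that course (42 + 21 = 63) is inside too. After a week-12 re-treatment, the first follow-up contact is the week-3 call (84 + 21 = 105), already outside.

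**Who lacks a clean first-course week-12 value.** The only follow-up clinic visit before week 12 is week 6, so the gap concerns patients re-treated at week 6. Their first-course week 12 is day 84, the same day as their second-course week-6 visit, so a FAOS is scheduled then but follows treatment 2.

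**The case against.** The strongest reply is that pooling is inferred. The objectives speak of measuring change after each treatment and V.A of testing each intervention; neither says that first and second courses are combined. The separate schedule for treatment 2 means the data are recorded apart and could be analysed apart. Specific Aim 1 concerns the nerves of the ankle in general, the sample size treats the 40 patients as one cohort, and no superficial-versus-deep comparison is planned. This stands in part: pooling is the plain reading, not an explicit statement. But a per-intervention analysis with no rule on course, sequence or baseline leaves the main choice open until the data are seen.

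A second reply is that all entrants are selected on pain (NRS of 5 or more), so regression to the mean affects first courses too, and that physical exam and eligibility are repeated at treatment 2, so the second nerve group might then be clinically indicated. Both are fair. Neither removes the selection on failure of the first course. The responder flowchart (Figure 2) is not shown and could not be checked.

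A reader might also infer that both nerve groups are still blocked at the primary endpoint of the second course. The documents do not support that. The 90 days is a hypothesised duration of pain relief, which the protocol says varies with the individual and the nerve, and not a measured block. Re-treated patients by definition have little relief. Second-course week 12 falls on day 126 or later.

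**Conclusion.** The point holds as one of attribution. Following V.A as worded, each nerve-group result, including week-12 FAOS-Pain, mixes first-line effects with add-on effects after non-response, and second-course change has no defined baseline. Possible overlap with the first treatment's relief is a lesser matter, confined among clinic visits to second-course week 6 after a week-6 re-treatment.

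The size depends on a split and a re-treatment rate that the plan does not give. Over the ranges shown, second courses are 20% to 60% of deep courses and about 8% to 33% of superficial courses. If re-treatment proves rare, the effect is small.

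It would go too far to conclude that the trial cannot meet its aims. First-course data remain usable, and the remedy lies in the analysis plan.

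**What to change.** State in II.A, Hypothesis 3a and V.A that superficial and deep effects, including week-12 FAOS-Pain, are estimated by first-treated nerve group, with every first-treated patient kept in the analysis.

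- For patients re-treated before week 12, use the FAOS-Pain from the re-treatment visit as the first-course value. The schedule already lists it at treatment 2; add that it is completed before the procedure. Run a sensitivity analysis with the observed week-12 value. Do not drop these patients: they are the early non-responders, and leaving them out would inflate the estimate. State a corresponding rule for week 24.
- Report second courses in a separate descriptive table by sequence (superficial then deep, deep then superficial), as change from the pre-treatment-2 value, labelled as added treatment after non-response. Do not pool them with first courses. Because that baseline is subject to regression to the mean, the table should not be read as a test of efficacy.

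The re-treatment rule is unchanged. The cost is wording, one table and one sensitivity analysis, and fewer courses per nerve group: 20 instead of 25 to 30 with a 20/20 split, or 10 deep instead of 17.5 to 25 with 30/10. After 20% dropout that leaves 16 per group (20 × 0.8), or 8 deep (10 × 0.8). At one-sided 0.025, before any multiplicity adjustment, a one-sample t-test has about 98% power with 16 patients at the protocol's FAOS-Pain effect size of 1.06, and 68% at its ADL effect size of 0.65. With 8 patients these become 73% and 36%. The overall cohort result for first courses does not depend on the split.

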FAOS (Pain, ADL, QoL), NRS for pain and physical performance tests (40 m fast paced walking test and, Standing Balance Test) will be assessed at baseline and 6, 12, and 24 weeks post-treatment. Phone calls at 3, 9 and 18 weeks post-treatment will monitor subjects using the NRS pain scale.⁷ Electronic data capture will be used for this study. Adverse events will be monitored at each telephone call and follow-up visit. There will be a grace period of 21 days between the screening and treatment visit. There is a +/- 3-day window for follow-up visits. During the time period of March to May, 2020(depending on duration of suspension of non-essential research), we are modifying the protocol to conduct virtual study visits to address the COVID-19 pandemic. The following data points will be or will not be collected during this time as per the individual circumstance: 40mFPWT or Standing Balance test at 6 week, 12 week, and 24 week. In order to ensure subject safety and welfare we will conduct the 6 week, 12 week and 24 week f/u visit remotely for each treatment arm as per KU essential research guidelines. We will also offer participants masks, gloves, and complete the f/u visit at the

earliest to limit any potential exposure to people in the hospital. In order to address data integrity issues, we will try to conduct the 12 week f/u visits in person.

[figure not shown]

Figure 2 – Protocol flowchart depicting criteria for responders and non-responders at each follow up time point.

C. Sample size and power calculation

In this open-label study, participants will undergo cryoneurolysis using iovera. FAOS (Pain, ADL, QoL), NRS for pain and physical performance tests (40m fast-paced walking test and Standing Balance Test) data will be collected at baseline and 6, 12 and 24 weeks post-treatment. A 24-week follow-up duration was selected to detect meaningful differences from standard of care and long-term effects. A control group will not be included in this initial pilot study. Differences between each of the three follow-up time points and baseline will be assessed using one-sample t-tests or repeated measures analyses, as appropriate, controlling for study-wide alpha level to account for multiple comparisons as well as 6-week and 24-week analyses.

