It has been found to be satisfactory in the measurement of many foot and ankle pathologies. The largest study of the FAOS to date is a registry-based study that found high internal consistency across the entire instrument, and high test-retest reliability in three of its five subscales. It has been specifically evaluated for the assessment of OA in another study. The purpose of this study was to verify the content validity, construct validity and responsiveness of the FAOS in patients with ankle OA.

The FAOS covers pain, other symptoms, activities of daily living (ADL), recreational function and quality of life. This outcome measure comprises of forty-two questions covering pain, disability, self-care and psychological factors. The minimum possible total score for each subscale is 0 points, whereas the score of 100 points represents the maximum score.

The primary endpoint of this study is the FAOS-Pain score compared to baseline at 12 weeks post-treatment.

FAOS - Pain

PAIN = 100 - (Total score P1-P9 x 100 / 36)

FAOS-Pain is a subscale of the Foot and ankle outcome score (FAOS) which is a self-reported outcome score. In our study, it will be the primary outcome measure. It comprises of the following questionnaire. The FAOS-Pain will be completed by the subject and will take approximately 3 minutes to complete. The study coordinator or designee will enter the data into the CRF.

P1. How often do you experience foot/ankle pain?

Never Monthly Weekly Daily Always

What amount of foot/ankle pain have you experienced the last week during the following activities?

P2. Twisting/pivoting on your foot/ankle

None Mild Moderate Severe Extreme

P3. Straightening foot/ankle fully

None Mild Moderate Severe Extreme

P4. Bending foot/ankle fully

None Mild Moderate Severe Extreme

P5. Walking on flat surface

None Mild Moderate Severe Extreme

P6. Going up or down stairs

None Mild Moderate Severe Extreme

P7. At night while in bed

None Mild Moderate Severe Extreme

P8. Sitting or lying

None Mild Moderate Severe Extreme

P9. Standing upright

None Mild Moderate Severe Extreme

Secondary Outcomes

FAOS - ADL

ADL = 100 - (Total score A1-A17 x 100/ 68)

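### The plan does not say how first-treatment outcomes are analysed once a non-responder has the other nerve group treated; week 24 is mainly exposed, the 12-week primary only through re-treatment at week 6

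*Combined protocol and SAP*

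**What the plan says.** - **Re-treatment (II.B).** A non-responder is "anyone reporting less than 20% pain relief with respect to their baseline NRS scores". Response is checked at clinic visits at weeks 6, 12 and 24 and remotely at weeks 3, 9 and 18. The rule is "For subjects who become non-responders, we will treat the other nerve group with iovera at their next clinic visit". The worked example is a week-9 non-responder after superficial treatment, where at week 12 "the participant will be offered treatment of the deep fibular nerve".
- **Endpoint.** I.A: "The primary study endpoint, clinically significant improvement in pain 12 weeks after each treatment, will be assessed using the FAOS-Pain subscale". II.A likewise measures change "at 6, 12 and 24 weeks after each superficial and deep treatment".
- **Analysis (II.C).** "Differences between each of the three follow-up time points and baseline will be assessed using one-sample t-tests or repeated measures analyses, as appropriate". V.A repeats this for each intervention, superficial and deep. II.C states that there is no control group.
- **Schedules (II.E).** The first table has FAOS at screening and at weeks 6, 12 and 24. A second table restarts at Treatment 2, with FAOS on that day and at weeks 6, 12 and 24, and NRS alone at the week-18 telephone contact.
- **Expected duration (I.B).** "The duration of the pain relief depends on the individual and the location of the nerve being treated"; about 90 days is hypothesised for the ankle.

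**The concern.** Nothing says whether first-treatment follow-up ends at re-treatment, or whether later values are kept, dropped or modelled. It is also not stated which baseline serves the second course, or whether the first schedule continues once the second begins. Analysing by intervention separates the two courses but does not assign a value collected after both treatments.

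The two simplest choices err in the same direction. Keeping the values adds whatever the second treatment contributes. Dropping the participants removes those selected for doing badly. A single-arm comparison with baseline has no second arm in which the error could cancel. What is at stake is the reported size of first-treatment relief and, where the true effect is small, the test conclusion.

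**Working it through.** **1. Which visits are exposed.** Applying the II.B rule to the visit schedule:

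| Non-response at | Re-treated at | First-treatment visits that follow re-treatment |
|---|---|---|
| Week 3 | Week 6 | Weeks 12 and 24 |
| Week 6 | Week 12 (week 6 if same-visit treatment is meant) | Week 24 (and week 12) |
| Week 9 | Week 12 | Week 24 |
| Week 12 | Week 24 (week 12 if same-visit) | None (week 24) |
| Week 18 | Week 24 | None |

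A FAOS taken on the day of re-treatment is largely protected, because items P2 to P9 ask "What amount of foot/ankle pain have you experienced the last week during the following activities". So the primary is reached only through re-treatment at week 6.

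**2. Overlap of the schedules, if the first one continues.** After re-treatment at week 12, first-course week 24 is second-course week 24 − 12 = 12. One FAOS-Pain value is then both a first-course late outcome and, under the I.A wording, a second-course primary outcome. After re-treatment at week 6, first-course week 24 is second-course week 24 − 6 = 18. The first table has a FAOS visit on that date; the second has an NRS-only telephone contact.

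**3. The plan's own figure.** No figure in the plan addresses re-treatment. The sample size of 32 is used below. By noncentral t at effect size 0.65, n = 32 gives 90.05% power at 0.0125 per side and 94.5% at 0.025 one-sided; 32/(1 − 0.20) = 40 enrolled. This has no bearing on the present point.

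**4. Shift in the mean.** Assumed, because the documents give neither: the share p re-treated, and the correlation r between early NRS relief and later FAOS-Pain change (0.3 to 0.5). In the working model the two are bivariate normal and the lowest p on NRS relief are re-treated.

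Dropping them: shift = r × φ(z_p)/(1 − p), in SD of change.
- p = 10%: r × 0.1755/0.9 = r × 0.195, giving +0.06 to +0.10
- p = 20%: r × 0.2800/0.8 = r × 0.350, giving +0.10 to +0.17
- p = 40%: r × 0.3863/0.6 = r × 0.644, giving +0.19 to +0.32

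Keeping their later values: shift = p × second-treatment gain. If that gain is 0.65 SD (assumed), the shifts are +0.07, +0.13 and +0.26. If the gain is zero, there is no shift.

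The 10% and 20% shares are the more relevant to week 12, which only re-treatment at week 6 can reach. The 40% share is relevant to week 24 only.

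**5. Test conclusion when the true effect is zero.** I simulated the same model with n = 32 and a one-sided t-test at 0.025. Dropping gave type I error of about 0.08 to 0.15 at 20% re-treated and 0.13 to 0.30 at 40%. Keeping, with the 0.65 SD gain, gave about 0.11 and 0.31 to 0.34. Allowing for simulation and rounding, the range is about 0.07 to 0.35. With 16 in a nerve group (an assumed equal split of 32), the mean shift is the same and the error is about 0.05 to 0.09 at 20% and 0.08 to 0.19 at 40%.

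Zero is plausible at week 24: that is day 168, against about 90 days of hypothesised relief. Someone re-treated at week 12 is then at day 84 of the second treatment, inside that window.

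**The case against.** The strongest reply is that the plan already treats the second treatment as a new course. The second table repeats consent, eligibility, FAOS, NRS and performance tests on the Treatment-2 day, and V.A analyses by intervention. This makes a separate second-course baseline the natural reading. It does not say what happens to the first course's later visits, so the gap stands.

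Several limits also stand:
- Every share and correlation above is assumed. II.B requires a diagnostic block that confirms analgesia before cryoneurolysis, which may lower early non-response, the main route to the primary.
- The double use of one FAOS value depends on the first schedule continuing, which is not stated.
- Figure 2 is not shown. Its caption covers responder criteria, so it may settle same-visit timing and the NRS item; the caption does not point to an analysis rule.
- This is an initial pilot, so the remedy should be short.

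A reader might infer that the 12-week primary is broadly contaminated, or that a shift of 0.32 SD applies to it. The timing table does not support that. The opposite inference, that the test result is safe because the anticipated effect is large, is not supported either: V.A analyses by nerve group, where numbers are smaller, and the anticipated effect says nothing about week 24.

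**Conclusion.** The omission can be read directly from the documents and should be fixed. Confidence is high for the missing rule and the ranking of visits, and low for the size. Under the stated assumptions, dropping re-treated participants overstates mean relief by roughly 0.06 to 0.17 SD at shares relevant to week 12, and by up to about 0.32 SD at 40% re-treated by week 24. Keeping later values overstates it only if the second treatment works. If the first treatment has worn off by week 24, either choice can turn a null result into an apparent long-term benefit. The documents do not support a claim that the re-treatment rule itself is wrong, or that the primary is invalid.

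**What to change.** Leave the re-treatment rule as it is and add analysis wording:

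1. Define the primary as FAOS-Pain change from the Visit 1 baseline to week 12 after the first treatment, in all treated participants, with one first-treatment record per person, by first treatment as V.A requires.
2. Do not use post-re-treatment values as first-treatment outcomes, and do not drop re-treated participants. Use the repeated-measures option already in the plan (mixed model or multiple imputation) on pre-re-treatment data. Include the NRS from every contact, because NRS triggers re-treatment, and use one NRS item throughout.
3. Add two sensitivity analyses: observed values regardless of re-treatment, labelled as the effect of the whole strategy; and one that lowers the modelled values of re-treated participants by a stated amount.
4. State which schedule governs FAOS collection after re-treatment. Report second-treatment outcomes separately as exploratory, with a named baseline, and give the number re-treated at each visit.

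Two side notes. II.E asks two NRS questions (past 7 days, right now), and the text does not say which decides responder status; Figure 2 may. In II.B, "For subjects who become non-responders, we will treat the other nerve group with iovera at their next clinic visit" and "the participant will be offered treatment of the deep fibular nerve" differ on whether re-treatment is given or offered and must be reconciled.

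The cost is a few paragraphs of text. The week-24 standard error will be wider. Some bias remains if uptake of re-treatment does not follow the recorded NRS, or if non-responders do worse than their NRS predicts; the second sensitivity analysis is there for that reason.
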